
Sample Size Calculation
	
First Co-Primary Endpoint: A sample size of 8 subjects/treatment group will provide 90% power to demonstrate a statistically significant difference between any AK002 dose group and placebo in achieving histologic response (defined as the peak esophageal intraepithelial eosinophil count ≤ 6 cells/hpf) at Week 24. This calculation is based on the AK002-003 study in which 90% of AK002 subjects and 10% of placebo subjects achieved the histologic response at Day 99. The hypothesized treatment effect of 80% yielded a small number of subjects per group for the first co-primary endpoint.
 
Second Co-Primary Endpoint: A sample size of 86 subjects/treatment group will provide 90% power to demonstrate a statistically significant difference between any AK002 dose group and placebo treatment group in mean absolute change in DSQ score from Baseline to Weeks 23–24. This calculation is based on the baseline score of 30 ± 15 (mean \pm Standard Deviation [SD]) reported in the literature, and an expected mean reduction of 15 in any AK002 dose group and 7.5 in the placebo group, and a SD of 15 for the change from baseline (Dellon, 2017; Hirano, 2019; Hudgens, 2017).
 
Consequently, approximately 100 subjects/treatment group will be included for a total of 300 subjects, driven by the second co-primary endpoint and potential 14% dropout rate.

Statistical Analysis
	
All subjects who received study medication will be included in the Safety Population for safety analysis. Subjects who are randomized and have received at least 1 dose of study medication will be included in the modified Intent-to-Treat (mITT) population for efficacy analysis.
 
Subjects who meet mITT criteria and do not have significant protocol deviations interfering with efficacy assessment will be included in the Per Protocol (PP) population.
 
The study statistician and study team will review protocol deviations to identify subjects to be excluded from the PP analysis population. The mITT population will be used for all efficacy analysis, and the PP population will be used for supplementary analyses of the primary endpoints and select secondary endpoints.

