--	---

Statistical Analysis cont.
	
Two sensitivity analyses will be conducted for the second co-primary endpoint. The first sensitivity analysis will be based on the placebo-based pattern-mixture model for the missing data imputation under the missing not at random (MNAR) assumption. In this model, subjects from the active treatment group after the ICE are assumed to behave like the subjects from the placebo group. Their missing data are imputed using the response profile from the placebo subjects who have similar baseline covariates and prior response trajectory. The second sensitivity analysis will utilize the tipping point method. In this method, the missing biweekly DSQ will be imputed with different adjustments for the active treatment subjects and placebo subjects under the MNAR assumption in search for a tipping point that reverses the study conclusion (i.e., p-value no longer <0.05 for the treatment effect).
 
Change in continuous outcomes will be analyzed using a mixed model for repeated measures (MMRM) and will include fixed effects for age, baseline value, treatment, visit, and the treatment by visit interaction and allow for random subject effects. Treatment and visit will each be fitted as categorical variables. The model will assume unstructured covariance structure. If the model with unstructured covariance does not converge or it is determined to be inappropriate as outlined in the Guerin and Stroup study (Guerin, 2000), then other covariance structures will be considered to model the within-subject errors. The selection of the covariance structure for the final model will be handled in a hierarchical fashion, with the order being heterogeneous Toeplitz, AR(1), and compound symmetry, respectively. The Kenward-Rogers approach for computing denominator degrees of freedom will be used to account appropriately for pooling of within and between-subject variance estimates. The least squares means with 95% CI will be presented for each treatment*week cross-classification.
 
A hierarchical procedure will be used to control the overall Type-I error rate at 0.05 for the primary endpoint and the secondary endpoints across the 2 AK002 dose regimens versus placebo. Each hypothesis will be formally tested only if the preceding hypothesis is significant at the 2-sided 0.05 significance level. The hierarchical testing order (all comparisons are with placebo) is detailed in the Statistical Analysis Plan.
 
Percent change in peak esophageal intraepithelial eosinophil count at Week 24 will be analyzed by ANCOVA with age strata, baseline eosinophil count, and baseline DSQ as covariates.
 
The proportion of subjects achieving peak esophageal intraepithelial eosinophil count of ≤ 1 eosinophils/hpf and < 15 eosinophils/hpf at Week 24 will each be analyzed using Fisher's exact test.

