15.2 Sample Size

To achieve statistical significance for the first co-primary endpoint, a sample size of 8 subjects per treatment group will provide 90% power to demonstrate a statistically significant difference between any AK002 dose regimens and placebo in achieving histological response (defined as ≤ 6 eosinophils/hpf at Week 24). This calculation is based on the AK002-003 study in which 90% of AK002 subjects and 10% of placebo subjects achieved a histologic response at Day 99. The hypothesized treatment effect of 80% yielded a small number of subjects per group for the first co-primary endpoint.

To achieve statistical significance for the second co-primary endpoint, a sample size of 86 subjects per treatment group will provide 90% power to demonstrate a statistically significant difference between any AK002 dose group and placebo group in mean absolute change in DSQ score from Baseline to Weeks 23–24. This calculation is based on the baseline score of 30 ± 15 (mean \pm SD) reported in the literature, and an expected mean reduction of 15 in the AK002 group and 7.5 in the placebo group, and a SD of 15 for the change from baseline (Dellon, 2017; Hirano, 2019; Hudgens, 2017).

Consequently, approximately 100 subjects per treatment group will be included for a total of 300 subjects, driven by the second co-primary endpoint and a potential dropout rate of 14%.

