### 3.6 Determination of Sample Size

To achieve statistical significance for the first co-primary endpoint, a sample size of 8 subjects per treatment group will provide 90% power to demonstrate a statistically significant difference between AK002 and placebo in achieving the histological response (defined as the peak esophageal intraepithelial eosinophil count  $\leq 6$  cells/hpf) at Week 24. This calculation is based on the AK002-003 study in which 90% of AK002 subjects and 10% of placebo subjects achieved the histologic response at Day 99. The hypothesized treatment effect of 80% yielded a small number of subjects per group for the first co-primary endpoint.

To achieve statistical significance for the second co-primary endpoint, a sample size of 86 subjects per treatment group will provide 90% power to demonstrate a statistically significant difference between any AK002 dose group and placebo treatment group in mean absolute change in DSQ score from baseline to Weeks 23–24. This calculation is based on the baseline score of  $30 \pm 15$  (mean  $\pm$  Standard Deviation [SD]) reported in the literature, and an expected mean reduction of 15 in the AK002 group and 7.5 in the placebo group, and a SD of 15 for the change from baseline (Dellon, 2021; Hirano, 2019; Hudgens, 2017).

Consequently, approximately 100 subjects per treatment group will be included for a total of 300 subjects, driven by the second co-primary endpoint and a potential 14% dropout rate.

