**Table 7 Hypothesis Testing Order Hierarchy**

Endpoint Description	AK002 IV Dose Groups	
	Low Dose	High Dose
Primary Endpoints		
1) The proportion of subjects who achieve a peak esophageal intraepithelial count of $\leq 6$ eosinophils/hpf at Week 24.	8	1
2) Mean change in DSQ score from Baseline to Weeks 23–24.		
Secondary Endpoints		
1) Percent change in peak esophageal intraepithelial eosinophil count at Week 24.	14	7
2) Proportion of subjects achieving peak esophageal intraepithelial eosinophil count of $\leq 1$ eosinophil/hpf at Week 24.	9	2
3) Proportion of subjects achieving peak esophageal intraepithelial eosinophil count of $< 15$ eosinophils/hpf at Week 24.	18	17
4) Proportion of treatment responders when a responder is a subject achieving $> 30\%$ reduction in symptoms (DSQ) at Weeks 23–24 and achieving a peak intraepithelial eosinophilic count of $\leq 6$ eosinophils/hpf at Week 24.	10	3
5) Proportion of subjects with $> 50\%$ reduction in DSQ score from Baseline to Weeks 23–24.	12	5
6) Percent change in DSQ score from Baseline to Weeks 23–24.	11	4
7) Change in biweekly mean DSQ over time.	16	15
8) Change in EoE Endoscopic Reference Score from Baseline to Week 24.	13	6

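### The 90% DSQ power is stated for any AK002 dose, but the Table 7 testing order delivers it only for the high dose

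*SAP*

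**What the plan says.** SAP 3.6 states for the second co-primary endpoint that "86 subjects per treatment group will provide 90% power to demonstrate a statistically significant difference between any AK002 dose group and placebo". Protocol 15.2 promises "90% power to demonstrate a statistically significant difference between any AK002 dose group and placebo group in mean absolute change in DSQ score", and the Synopsis has "A sample size of 86 subjects/treatment group will provide 90% power to demonstrate a statistically significant difference between any AK002 dose group and placebo". The effect is assumed equal for both doses: the Synopsis gives "an expected mean reduction of 15 in any AK002 dose group and 7.5 in the placebo group", with an SD of 15 for the change. The target of 86 becomes about 100 randomised per arm after a 14% dropout allowance.

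The testing rule is in the Synopsis, Protocol 15.7 and SAP 5.8: "Each hypothesis will be formally tested only if the preceding hypothesis is significant at the 2-sided 0.05 significance level". SAP Table 7 ("Hypothesis Testing Order Hierarchy") runs one sequence across both doses:

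- Step 1: high-dose co-primaries (histology and DSQ change).
- Steps 2 to 7: six high-dose secondaries. Step 4 is percent change in DSQ and step 5 is more than 50% DSQ reduction.
- Step 8: low-dose co-primaries.

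None of the three sample-size texts mentions this order. No power is given for the secondaries that gate the low dose, or for the low dose within the sequence.

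**The concern.** The sample-size sentence offers 90% power for either dose. The calculation behind it is a single two-group test at two-sided 0.05. The high dose at step 1 meets that condition. The low dose does not, because its formal test exists only if eight earlier endpoint tests all succeed (two co-primaries at step 1 and six secondaries).

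The low dose could reach p<0.05 on both co-primaries and still support no formal claim because one high-dose secondary missed. The sample-size section does not show how likely that is. Step 5 is a particular risk, since it dichotomises the same DSQ data and so has less power than the continuous analysis.

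**Working it through.** **Inputs.** Difference 15 − 7.5 = 7.5, SD 15, two-sided 0.05, 14% dropout (SAP 3.6); 1:1:1 allocation with one placebo arm (SAP 3.3.3); testing order from SAP Table 7.

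**1. Reproduce the plan's figure.** n = 2(z₀.₉₇₅ + z₀.₉₀)² × SD²/difference² = 2 × (1.960 + 1.282)² × 225/56.25 ≈ 84.1, so 85 by normal approximation. The noncentral t needs 86 (power 0.8999 at 85, 0.903 at 86, 0.940 at 100). Dropout: 86/0.86 = 100. The stated N is correct for one comparison. At 90% versus 10% response, Fisher power at 86 per arm is essentially 1, so step 1 power is the DSQ power, about 90%.

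**2. Both doses' DSQ tests significant, with steps 2 to 7 certain to pass.** Each dose-placebo contrast has variance 2σ²/n. The shared placebo arm gives covariance σ²/n, so the two statistics correlate at 0.5.

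- At 86: 7.5/(15√(2/86)) = 3.279, and 3.279 − 1.960 = 1.319. Single power Φ(1.319) = 0.906; joint Φ₂(1.319, 1.319; 0.5) = **0.842**.
- At 100: 3.536 − 1.960 = 1.576. Single power 0.942; joint **0.900**.
- Simulated t-tests (100,000 trials) give 0.835 and 0.896.

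**3. Let high-dose steps 4 and 5 fail as well.** Common assumptions: baseline N(30, 15) restricted to 12–84 (entry requires at least 12); mean changes −15, −15 and −7.5 with SD 15; ANCOVA for change and percent change; stratified CMH for more than 50% reduction; steps 2, 3, 6 and 7 always pass. The baseline-change correlation is not in the documents, so it is varied. The set-ups differ as follows:

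- A: follow-up clipped to 0–84, CMH by baseline DSQ only, 3,000 trials.
- B: bivariate normal before the baseline cut, clipped, four-stratum CMH with an assumed 20% adolescents, 1,500 trials.
- C: no clipping, so the 7.5 difference is kept; four-stratum CMH, 1,500 trials.

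Probability of a formal low-dose DSQ win:

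| Set-up | n per arm | ρ = 0 | −0.3 | −0.5 | −0.6 |
|---|---|---|---|---|---|
| A | 86 | .61 | .69 | .80 | .82 |
| B | 86 | .57 | .71 | .81 | .86 |
| C | 86 | .61 | .68 | .78 | .83 |
| A | 100 | .68 | .79 | .85 | .90 |
| B | 100 | .70 | .76 | .85 | .92 |
| C | 100 | .70 | .75 | .86 | .92 |

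Clipping shrinks the difference to about 6.4–7.2 in A and B. C does not clip and gives similar results, so clipping is not the cause. Further runs with simpler coding fall in the same ranges, except for 0.89 at 100 per arm and ρ = −0.6. Monte Carlo standard error is about 1 point: √(.57 × .43/1500) = 0.013.

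Step 5 alone in C succeeds with probability .68/.74/.83/.86 at 86 and .74/.80/.88/.93 at 100, across the four correlations. In every setting the gated low-dose figure is 8 to 30 points below ungated low-dose power in the same setting.

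**The case against.** **Pairwise wording.** The sentence can be read as ordinary per-comparison power, and on that reading it is true for each dose. The order is also disclosed in SAP Table 7. Both points stand: there is no arithmetic error and no hidden rule. But step 8 of a strict sequence is not a stand-alone comparison, and the text does not say which kind of power it reports. Reading the sentence as at least one dose does not help. That probability is about 97% unadjusted at 86 per arm, but the hierarchy allows no such test: if the high dose fails step 1, the low dose is never formally tested.

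**ANCOVA.** The planned analysis adjusts for baseline DSQ, so 84% is not a ceiling. Residual SD is 15√(1 − ρ²): 13.7 at ρ = −0.4 and 13.0 at ρ = −0.5. Joint DSQ success before steps 2 to 7 is then about 91% and 94% at 86 per arm, and 95% and 97% at 100. This stands. The simulations already use ANCOVA, however, and with 86 per arm step 5 still holds the gated figure below 90% in every setting.

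**Plausibility of the low figures.** Zero correlation implies a follow-up SD of √(225 + 225) = 21.2 around an active-arm mean of 15. That would put about 24% of subjects below zero on a score that cannot be negative. Equal SDs of 15 at baseline and follow-up imply ρ = −0.5, where the gated figures are .78–.81 at 86 and .85–.86 at 100. The entry cut also moves baseline to about 33.3 ± 12.4, so a 15-point fall is about 45% of the mean and not 50%, which tends to lower step 5. These are fair cautions about the low end of the range. They do not restore 90% at the stated 86.

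**Conclusion.** The concern holds. The 90% at 86 per arm is correct per-comparison power and, under SAP 5.8 and Table 7, is delivered for the high dose at step 1 only.

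On the plan's inputs with an unadjusted test, joint DSQ success for both doses is 84% at 86 and 90% at 100, before any loss at steps 2 to 7. When high-dose steps 4 and 5 must also succeed, the simulated formal low-dose DSQ win is 57–81% at 86 and 68–86% at 100 for correlations from 0 to −0.5. At −0.6 it is 82–86% and about 89–92%.

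The gated figures are illustrative and are not bounds, because they rest on an unstated correlation and an assumed baseline distribution. They are generous in one respect: steps 2, 3, 6 and 7 never fail, although step 3 also uses DSQ. The mislabelled power is certain; the exact size of the shortfall is not. The plan should be corrected on this point, but the design remains valid and Type I error control is not in question.

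**What to change.** In the Synopsis, Protocol 15.2 and SAP 3.6, state that 90% is the power of a single dose-placebo comparison and that, within the hierarchy, it applies to the high dose at step 1. Add the low-dose power under the Table 7 order from the sponsor's own simulation, with its assumptions: evaluable n per arm, baseline-change correlation, and success rates for the non-DSQ steps.

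The order is the sponsor's choice and need not change. The cost is one or two sentences in three places and one simulation. One stated figure becomes less favourable, and no patients are added.

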## 4. Definitions

### 4.1 Terminology and Definitions

**Table 2 Terminology and Definitions**

Terminology	Definition
Baseline	Baseline for non-daily assessment (e.g., laboratory tests and CCI ) is defined as the non-missing value collected most recent to and before the time of the first dose of study drug. This includes lab tests collected on Day 1 Predose as an example. Baseline DSQ score is determined from 14 days prior to the first dose.
Completer for the Study	
A subject who does not participate in the OLE period and who completes visits through the Day 197 visit or, if applicable, the last Extended Follow-Up visit after completing Day 197, will be recorded as having completed the double-blind portion of the study.
 
A subject who completes visits through the Day 169 visit and participates in the OLE period of the study will be recorded as having completed the double-blind portion of the study.
 
A subject who participates in the OLE period of the study and completes visits through the Day 372 visit or, if applicable, the last Extended Follow-Up visit after completing Day 372 will be recorded as having completed the OLE portion of the study.

Concomitant Medication	Medication collected on the Prior/Concomitant Medication CRF with end date on/after Study Day 1. Note a Prior Medication may also be a Concomitant Medication if the start date is prior to Study Day 1 and end date is on/after Study Day 1.
DSQ	Dysphagia Symptom Questionnaire: See Appendix 1 for the DSQ and the DSQ scoring algorithm.
EG/EoD Subject-Reported Outcome (PRO)	
PRO questionnaire evaluates 8 different symptoms with 10 daily questions for intensity and frequency:
 
 
• Abdominal pain intensity
 
• Nausea intensity
 
• Vomiting intensity
 
• Vomiting frequency
 
• Diarrhea intensity
 
• Diarrhea frequency
 
• Early satiety intensity
 
• Loss of appetite intensity
 
• Bloating intensity
 
• Abdominal cramping intensity
 
 
Each intensity evaluation is scored on a scale of 0=none to 10=worst possible.

**Table 2 Terminology and Definitions cont.**

Terminology	Definition
Enrolled	Subject who is randomized to a treatment group.
CCI	: See Appendix 1 .
EREFS	EoE Endoscopic Reference Score: See Appendix 1 .
Newly Initiated Medication	Refers to any medication with start date $\geq$ Study Day 1.
Prior Medication	Medication collected on the Prior/Concomitant Medication CRF with start date prior to Study Day 1.
PRO TSS	Total Symptom Score is the sum of 6 weekly average symptom intensity scores (abdominal pain, abdominal cramping, bloating, nausea, early satiety, and loss of appetite).
TEAE	Treatment-emergent adverse events reported in the clinical database with a date of onset on or after the start date of the first dose of the study drug.
Tissue Eosinophil Responder	For subjects who achieve a peak esophageal intraepithelial count of $\leq 6$ eosinophils/hpf at Week 24
Treatment Responder	Subjects who achieve a peak esophageal intraepithelial count of $\leq 6$ eosinophils/hpf at Week 24 and achieve $>30\%$ reduction in biweekly DSQ score at Weeks 23–24.
Study Day	Study Day 1 is defined as the date on which a subject took the first dose of Study Drug. Other study days are defined relative to Study Day 1. For visits prior to the first dose of Study Drug, Study Day is calculated as Visit Date – Day 1 Date. For visits after the first dose, Study Day is calculated as Visit Date – Day 1 Date +1.
Study Drug	AK002 or placebo administered by IV infusion.
Study Week	Defined as 7 days a week starting from the day of first dose (Day 1).

